#### **12.2.4 Partial Response (PR)**

PR requires one of the following:

- Greater than or equal to 50% reduction in the level of the serum monoclonal paraprotein and reduction in 24 hour urinary monoclonal paraprotein either by greater than or equal to 90% or to <200 mg/24 hours in light chain disease.
- If the only measurable non-bone marrow parameter is FLC, greater than or equal to 50% reduction in the difference between involved and uninvolved FLC levels or a 50% decrease in level of involved FLC with 50% decrease in ratio,
- If the bone marrow is the only measurable parameter, greater than or equal to 50% reduction in bone marrow plasma cells given that the baseline count was greater or equal to 30%,
- Greater than or equal to 50% reduction in the size of soft tissue plasmacytomas if present at baseline (by radiography or clinical examination).

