#### **12.2.2 Complete Response (CR):**

CR requires *all* of the following:

- Absence of the original monoclonal paraprotein in serum and urine by routine electrophoresis and by immunofixation. The presence of new monoclonal bands consistent with oligoclonal immune reconstitution does not exclude CR.
- Less than 5% plasma cells in a bone marrow aspirate and also on trephine bone biopsy, if biopsy is performed.

- No increase in size or number of lytic bone lesions on radiological investigations (development of a compression fracture does not exclude CR)\*.
- Disappearance of soft tissue plasmacytomas.

\*If not clinically indicated, radiographs are not required to document CR.

Patients in whom some, but not all, the criteria for CR are fulfilled are classified as partial responses (see below), providing the remaining criteria satisfy the requirements for partial response. This includes patients in whom routine electrophoresis is negative but in whom immunofixation has not been performed.

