As a secondary clinical endpoint, response will be assessed according to IMWG response criteria. In a prior phase I trial of DC/MM vaccination in patients with relapsed MM, 69% (11/16) patients had disease stabilization. No patients demonstrated disease response (PR, VGPR, or CR). In the present phase II trial, overall response rate per IMWG criteria will be assessed. An exact binomial test with a 10% one-sided significance level will have 82% power to detect the difference between the ORR proportion of 0.15 (null hypothesis) and the alternative ORR proportion of 0.35 when the sample size is 25. An ORR of 35% is considered worthy of further study in a larger trial.

If 3 or more patients experience a TLT, accrual will be suspended.

	True but Unknown Rate of DLT				
	0.10	0.20	0.25	0.30	0.40
Probability of continuation of enrollment ( $\leq 2$ TLT in 10 pts)	0.930	0.678	0.526	0.383	0.167

If the true rate of TLT is 25%, the probability of observing 2 or fewer TLTs within a cohort of 10 patients is 0.526.

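### Section 12.2.4 lets plasmacytoma shrinkage alone count as a partial response, which does not fit the neighbouring criteria and can inflate the secondary ORR test

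*Combined protocol and SAP*

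**What the plan says.** Section 12.2.4 introduces the PR criteria with "PR requires one of the following". Four items follow:

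- Paraprotein: "Greater than or equal to 50% reduction in the level of the serum monoclonal paraprotein and reduction in 24 hour urinary monoclonal paraprotein", with a threshold for the urine part.
- Free light chains, restricted by "If the only measurable non-bone marrow parameter is FLC".
- Marrow plasma cells, restricted by "If the bone marrow is the only measurable parameter".
- Plasmacytomas: "Greater than or equal to 50% reduction in the size of soft tissue plasmacytomas if present at baseline", judged by radiography or clinical examination.

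Section 12.2.2 (CR) requires all of its items, and one of them is "Disappearance of soft tissue plasmacytomas". Section 12.2.7 counts a serum paraprotein rise as progression only if it exceeds 25% and is also at least 0.5 g/dL in absolute terms. It also counts a definite increase in existing plasmacytomas, or new ones, as progression.

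Section 1.3.2 counts CR, VGPR and PR as clinical response. Section 14.1 tests ORR with a one-sided 10% exact binomial test of 0.15 against 0.35 with 25 patients, states 82% power, and adds: "An ORR of 35% is considered worthy of further study in a larger trial". It refers to IMWG criteria, whereas Section 12.1 refers to the International Uniform Response Criteria.

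**The concern.** The first three PR items work as substitutes for one another: paraprotein, or FLC when it is the only measurable parameter outside the marrow, or marrow when nothing else can be measured. The fourth item is different. Its only condition is that a plasmacytoma existed at baseline, and it asks nothing of paraprotein, FLC or marrow. Under a one-of rule it is therefore sufficient by itself.

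Two kinds of patient are then counted as responders:

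- A patient whose plasmacytoma halves while serum paraprotein is flat, falls by less than half, or rises by less than the Section 12.2.7 threshold.
- A patient whose paraprotein meets its PR threshold while a baseline plasmacytoma does not shrink, provided it does not definitely increase.

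If the rise in paraprotein does reach the progression threshold while the plasmacytoma halves, the patient meets both PR and PD, and Section 12.2.4 does not say which takes precedence.

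ORR is the only clinical endpoint with a stated hypothesis test, and its result is tied to a recommendation for a larger trial.

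**Working it through.** **1. How the sections fit together.**

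- In Section 12.2.4 two of the four items carry an only-measurable condition. The plasmacytoma item carries none, so it does not act as a fallback for patients without a marker.
- In Section 12.2.2 plasmacytoma disappearance must be met alongside the marker and marrow items. Section 12.2.2 also allows an incomplete CR to be classed as PR only if the remaining criteria meet the PR requirements. That suggests a joint standard, but the one-of rule in Section 12.2.4 does not deliver it.
- Section 3.2.2 excludes purely non-secretory disease. Every enrolled patient should therefore have a serum M protein, urine Bence-Jones protein or an involved FLC above 100 mg/L. There is no evident need for a plasmacytoma-only route.

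**2. Direction of the effect.** Any patient who meets a joint rule (a marker or marrow item, plus plasmacytoma reduction if lesions were present) also meets the one-of rule. The reverse is not true. On the same data, the ORR under the one-of rule can only be equal or higher.

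**3. The plan's own figure.** Inputs from Section 14.1: n = 25, null 0.15, alternative 0.35, one-sided 10%, exact binomial. The cut-off is not stated, so it is the smallest r with P(X ≥ r | 25, 0.15) ≤ 0.10.

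- r = 6: P(X ≥ 6 | 0.15) = 0.1615, above 0.10.
- r = 7: P(X ≥ 7 | 0.15) = 0.0695; power P(X ≥ 7 | 0.35) = 0.8266.

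Success therefore means 7 or more of 25, and the stated 82% is reproduced.

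**4. Sensitivity.** The documents give no plasmacytoma frequency, so this step rests on an assumption. Let f be the share of true non-responders who qualify through plasmacytoma shrinkage alone. At a true ORR of 15%, the apparent ORR is 0.15 + 0.85 × f. The mean number wrongly counted is 25 × 0.85 × f.

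| f | Apparent ORR | Mean number wrongly counted | P(X ≥ 7) |
|---|---|---|---|
| 0 | 0.1500 | 0 | 0.070 |
| 1% | 0.1585 | 0.21 | 0.088 |
| 2% | 0.1670 | 0.43 | 0.110 |
| 3% | 0.1755 | 0.64 | 0.135 |
| 5% | 0.1925 | 1.06 | 0.192 |
| 10% | 0.2350 | 2.13 | 0.370 |

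The nominal 0.10 is crossed between f = 1% and f = 2%.

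**5. Effect of a single patient.** If exactly one non-responder is wrongly counted, 6 true responders are enough, and the false-positive chance is about 0.162. If two are, 5 are enough, and it is about 0.318.

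**The case against.** **A named standard may govern.** Section 14.1 cites IMWG criteria, and Sections 5.14 and 5.15 use IMWG for progression. On that view Section 12.2.4 is a loose summary and nobody need be misclassified. This is a fair point, and it rules out one stronger reading. A reader might infer that the resulting rate is not the IMWG ORR, but the IMWG text is not in the documents, so that cannot be checked. The conflict remains all the same: Section 12.2 is the only place where the categories are defined, and assessors working from different texts could classify the same patient differently.

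**Different connectors do not show which is wrong.** CR says all and PR says one of, so the comparison with CR alone does not settle the matter. The case also rests on the restricted FLC and marrow items and on Section 3.2.2. One reservation stands: a detectable marker is not always a measurable one. If a plasmacytoma-only route is meant for such patients, it should carry the same kind of restriction as the FLC and marrow items.

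**The effect may be small.** It needs a plasmacytoma at baseline, shrinkage of at least half, and no marker response, all in the same patient. Eligibility does not select for plasmacytomas. This stands. A reader might assume that 1 or 2 patients in 25 are misclassified, which would raise the chance of success to 0.183 (apparent ORR 19%) or 0.347 (23%). In terms of f that is 0.04/0.85 = 4.7% and 0.08/0.85 = 9.4%. Nothing in the documents supports starting the range there, and at f = 1% the chance is still below the nominal 0.10.

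**VGPR.** A reader might infer that the looser PR also inflates VGPR. It does not: Section 12.2.3 requires a further paraprotein or light-chain criterion.

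**Growing lesions.** A reader might infer that a paraprotein PR survives an enlarging plasmacytoma. Section 12.2.7 makes a definite increase progression, so only stable lesions, or lesions shrinking by less than half, are affected.

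**Sparse imaging.** Imaging is scheduled before enrollment, again before immunotherapy only if needed, and then at follow-up months 1 and 6. None is scheduled in cycles 1 to 6. This makes plasmacytoma-only PRs rarer, and it also means that a joint rule has a cost. Both points stand.

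**Conclusion.** The point holds as an internal inconsistency in a stated rule. Followed as written, Section 12.2.4 counts as responders some patients whose marker has not responded, and some whose baseline plasmacytoma has not shrunk. The bias in ORR can only be upward.

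Its size is unknown, because the documents do not say how many patients have plasmacytomas. For f of 1%, 2% and 5%, the false-positive chance at a true ORR of 15% moves from 0.070 to 0.088, 0.110 and 0.192. These figures assume 25 evaluable patients, independent outcomes, the 7-of-25 cut-off derived above, and the plasmacytoma-only route alone. The opposite case (marker response without plasmacytoma shrinkage) is not quantified.

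The reach is limited to a secondary endpoint. A reader might infer that the trial's main conclusion is at risk, but the primary immunologic rule in Section 14.1 (17 or more of 25) does not use response categories. The wording should be corrected because the test has little room: one wrongly counted responder is enough to take it past its 10% level.

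**What to change.** - **Section 12.2.4:** keep the paraprotein, FLC-only and marrow-only items as alternatives. Add that, if soft tissue plasmacytomas were present at baseline, a reduction of at least 50% in their size is required as well.
- **Section 14.1:** state that ORR is counted by Section 12.2 as reworded, and reconcile this with the IMWG reference there and the International Uniform Response Criteria in Section 12.1.

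**Cost:** a sentence in each section, with no change to sample size or to the test. The observed ORR may be slightly lower. For lesions that cannot be assessed by examination, PR may be confirmed only at the next scheduled imaging, at follow-up month 1 or 6, so some marker responders would be classed as PR later than they are now.

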#### **12.2.5 Stable Disease (SD)**

- Patients who do not meet criteria for sCR, CR, VGPR, partial response or progressive disease (section 3.1.1.2) are considered to have stable disease (SD).

#### **12.2.6 Disease Progression (PD)**

Progression from CR or sCR requires one or more of the following:

- A reappearance of serum monoclonal paraprotein, with a level of at least 0.5 g/dL.
- 24-hour urine protein electrophoresis with at least 200 mg paraprotein/24 hours.
- Abnormal FLC levels of >10 mg/dL, only in patients without measurable paraprotein in the serum and urine.
- At least 10% plasma cells in a bone marrow aspirate or on trephine biopsy.
- Definite increase in the size of existing bone lesions or soft tissue plasmacytomas.
- Development of new bone lesions or soft tissue plasmacytomas.
- Development of hypercalcemia (corrected serum Ca >11.5 mg/dL or >2.8 mmol/L) not attributable to any other cause.

#### **12.2.7 Progressive Disease (PD)**

For patients not in CR or sCR, progressive disease requires one or more of the following measured from the time of randomization:

- >25% increase in the level of the serum monoclonal paraprotein, which must also be an absolute increase of at least 0.5 g/dL.

- >25% increase in 24-hour urine protein electrophoresis, which must also be an absolute increase of at least 200 mg/24 hours.
- Absolute increase in the difference between involved and uninvolved FLC levels (absolute increase must be >10 mg/dL), only in patients without measurable paraprotein in the serum and urine.
- >25% increase in plasma cells in a bone marrow aspirate or on trephine biopsy, which must also be an absolute increase of at least 10%.
- Definite increase in the size of existing bone lesions or soft tissue plasmacytomas.
- Development of new bone lesions or soft tissue plasmacytomas.
- Development of a compression fracture does not exclude continued response and may not indicate progression.
- Development of hypercalcemia (corrected serum Ca >11.5 mg/dL or >2.8 mmol/L) not attributable to any other cause.

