#### 3.2 Exclusion Criteria

3.2.1 Participants who are receiving any other investigational agents.

3.2.2 Participants with purely non-secretory MM [absence of a monoclonal protein (M protein) in serum as measured by electrophoresis and immunofixation and the absence of Bence-Jones protein in the urine defined by use of conventional electrophoresis and immunofixation techniques and the absence of involved serum free light chain >100 mg/L]. Patients with light chain MM detected in the serum by free light chain assay are eligible.

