### **5.14 Criteria for Taking a Participant Off Treatment**

Duration of therapy will depend on individual response, evidence of disease progression and tolerance. In the absence of treatment delays due to adverse event(s), treatment may continue for up to 6 cycles of nivolumab or until one of the following criteria applies:

- Disease progression by IMWG criteria, after the administration of study treatment
- Intercurrent illness that prevents further administration of treatment
- Unacceptable adverse event(s)
- Participant demonstrates an inability or unwillingness to comply with the oral medication regimen and/or documentation requirements
- Participant decides to withdraw from the protocol therapy
- General or specific changes in the participant's condition render the participant unacceptable for further treatment in the judgment of the treating investigator

Participants will be removed from the protocol therapy when any of these criteria apply. The reason for removal from protocol therapy, and the date the participant was removed, must be documented in the case report form (CRF). Alternative care options will be discussed with the participant.

When a participant is removed from protocol therapy and/or is off of the study, the relevant Off-Treatment/Off-Study information will be updated in OnCore.

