## **12. MEASUREMENT OF EFFECT**

### **12.1 Definition of Disease Status**

Patients' disease status at each data collection period will be evaluated based on the International Uniform Response Criteria. Until disease progression, all disease classifications are relative to the patient's disease status prior to autologous transplant (i.e. study entry). At time of disease progression, disease classifications are relative to the patient's best response since time of study entry.

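### The free-light-chain progression item has no relative threshold, so a stable light-chain-only patient with a high level can be counted as a PFS event on a rise below 25%

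*Combined protocol and SAP*

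**What the plan says.** Section 12.2.7 lists the ways in which a patient not in CR or sCR can progress. One item is enough. Three of the four numerical disease-burden items have two parts:

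- Serum: ">25% increase in the level of the serum monoclonal paraprotein, which must also be an absolute increase of at least 0.5 g/dL".
- Urine: ">25% increase in 24-hour urine protein electrophoresis, which must also be an absolute increase of at least 200 mg/24 hours".
- Marrow: ">25% increase in plasma cells in a bone marrow aspirate or on trephine biopsy, which must also be an absolute increase of at least 10" percent.

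The fourth has one part: "Absolute increase in the difference between involved and uninvolved FLC levels (absolute increase must be >10 mg/dL), only in patients without measurable paraprotein" in serum and urine.

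Section 3.2.2 allows such patients to enter: "Patients with light chain MM detected in the serum by free light chain assay are eligible". It sets no upper limit on the FLC level. Section 12 asks for no confirmatory reading, and no other section supplies a relative FLC condition for progression. The FLC response rules are relative: a 50% reduction for PR (12.2.4) and 90% for VGPR (12.2.3).

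PFS is a secondary clinical endpoint (1.3.2). Section 14 gives it no hypothesis or power.

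**The concern.** A fixed rise of 10 mg/dL is a large change for a patient at 15 mg/dL and a small one for a patient at 200 mg/dL. At high levels, measurement and biological variation alone could exceed it. The same list guards against this for serum, urine and marrow by adding a percentage, but not for FLC.

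The stake is PFS. False events would shorten it in light-chain-only patients, and progression would mean something different by disease type. With 25 evaluable patients, each misclassified patient is 1/25 = 4% of the sample. There may be knock-on effects if section 12.2.7 is also used to decide who starts vaccination (3.3.3), who stops treatment (5.14) or who leaves the study (5.15). Patients removed for progression do not have the monthly active follow-up visits (5.11), so later immune samples would be lost.

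**Working it through.** The plan derives no figure from this rule, so there is none to reproduce.

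**Inputs from the documents.** Absolute floor 10 mg/dL and 25% relative threshold (12.2.7). FLC measured on day 1 of every cycle (5.6, 5.9), which gives five on-treatment tests after cycle 1.

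**Assumptions, not in the documents.** True involved-minus-uninvolved difference L constant, from 20 to 200 mg/dL. Independent visit-to-visit variation (assay plus biology) with CV 5, 10 or 15%.

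**Step 1. Relative size of the threshold: 10/L.**

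- L = 20: 10/20 = 50%
- L = 40: 10/40 = 25%
- L = 100: 10/100 = 10%
- L = 200: 10/200 = 5%

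The FLC item is looser than the other three only above 40 mg/dL.

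**Step 2. One later reading against one baseline reading, normal errors.** The difference of two readings has SD = L × CV × √2, so P(false progression) = 1 − Φ(10/SD) as written. The paired form replaces 10 by max(10, 0.25L).

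- L = 100, CV 10%: SD = 14.14. As written, 1 − Φ(0.707) = 0.240. Paired, 1 − Φ(25/14.14) = 0.039.
- L = 100, CV 5%: SD = 7.07. As written, 1 − Φ(1.414) = 0.079. Paired, below 0.001.
- L = 40, CV 10%: SD = 5.66. Both rules, 1 − Φ(1.768) = 0.039.

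**Step 3. At least one false progression over five tests.** Simulation with log-normal readings, no true change, and the baseline reading as reference (400,000 patients per cell).

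| L (mg/dL) | CV | As written | Paired | Difference |
|---|---|---|---|---|
| 40 | 5% | 0.001 | 0.001 | 0.000 |
| 40 | 10% | 0.147 | 0.145 | 0.001 |
| 40 | 15% | 0.362 | 0.355 | 0.007 |
| 100 | 5% | 0.252 | 0.004 | 0.248 |
| 100 | 10% | 0.566 | 0.185 | 0.381 |
| 100 | 15% | 0.674 | 0.388 | 0.286 |
| 200 | 5% | 0.560 | 0.004 | 0.556 |
| 200 | 10% | 0.717 | 0.184 | 0.533 |
| 200 | 15% | 0.762 | 0.388 | 0.374 |

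Differences are taken before rounding. The difference column is the part due to the missing relative condition. The paired column is the error left by single unconfirmed readings, to which the paired items are also open.

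**Step 4. Reference point.** Section 12.2.7 says "progressive disease requires one or more of the following measured from the time of randomization", although the study describes no randomization. Section 12.1 says "At time of disease progression, disease classifications are relative to the patient's best response since time of study entry". If the second is read as the lowest reading so far, the as-written probabilities rise. With normal errors, L = 100 and five tests they are 0.529, 0.898 and 0.959 at CV 5, 10 and 15%, against 0.012, 0.432 and 0.748 paired. The baseline reference in step 3 therefore gives the lower false-progression rates.

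**Step 5. Scale.** If m patients have L near 100 mg/dL and no measurable paraprotein, the expected extra false events are about 0.25m to 0.38m. For an assumed m of 2, that is 0.5 to 0.8 events.

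**The case against.** The strongest reply is about reach. The item covers only patients without measurable paraprotein in both serum and urine; a light-chain patient with measurable urine paraprotein falls under the paired urine item. The large effects need levels of 100 mg/dL or more, in patients who have also come through bridging therapy without progression. The documents do not show that any of the 25 would fit. This stands: the textual gap is certain, its impact is not.

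Four stronger readings are tempting, and the documents do not support them.

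- *Every stable patient with a high level will be called progressed.* At 100 mg/dL and CV 5%, the five-test probability is 0.25. The supportable wording is "can be".
- *All of that probability comes from the missing percentage.* At 100 mg/dL and CV 15%, 0.388 of 0.674 remains under the paired form.
- *The primary result is compromised.* The rule of 17 or more of 25 (section 14.1) counts immune responses and does not use progression. Blood and marrow samples are still taken at progression (10.1, 10.2); only later ones are lost.
- *Patients will be taken off treatment by this item.* Section 5.14 says "Disease progression by IMWG criteria, after the administration of study treatment" and does not cite 12.2.7. Section 14.1 also names IMWG for response, and 12.1 names the International Uniform Response Criteria. Those sources are not in the documents, so it cannot be said whether the FLC item departs from them or would drive section 5.14.

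The citation of IMWG does not dispose of the point, because section 12 is the only place where progression is spelled out.

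**Conclusion.** The point holds for PFS. As written, section 12.2.7 can count a stable patient as progressed on a 10% rise at 100 mg/dL or a 5% rise at 200 mg/dL. At 100 mg/dL the missing relative condition adds about 0.25, 0.38 or 0.29 to the five-test false-progression probability at CV 5, 10 or 15%. At 40 mg/dL or below the two forms are practically the same. These figures rest on the assumed CVs, independent errors, a constant true level and a baseline reference. The direction does not depend on the chosen CV; the total effect on PFS depends on a subgroup size that the documents do not give. This should be fixed, but it does not threaten the primary decision rule.

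**What to change.** For the PFS endpoint definition, write the FLC item in the form that the list already uses three times: an increase of more than 25% in the involved-minus-uninvolved difference, together with the existing absolute rise of more than 10 mg/dL. State one reference point for it, since 12.1 and 12.2.7 differ. At minimum, keep the current item and report PFS under the paired form as a sensitivity analysis, using the FLC values already collected. No FLC-only confirmation requirement is proposed: it would itself make progression differ by disease type, and the toxicity visit after removal for progression (5.11.3) has no FLC test.

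The cost is one line of text and no new tests. Some PFS events in FLC-only patients will be dated later. The sensitivity analysis has a limit: patients removed for progression have no scheduled FLC values after the progression assessment, so some would have to be censored there. The follow-up calendar in section 11 marks FLC, while the visit lists in 5.11.1 and 5.11.2 omit it; these need to agree.

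For starting vaccination (3.3.3), stopping treatment (5.14) and leaving the study (5.15), the sponsor should reconcile section 12.2.7 with the criteria cited in 5.14, 5.15, 12.1 and 14.1. No clinical rule is proposed here.
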